## 6. TREATMENT PLAN

### 6.1 Agent Administration

Treatment will be administered on an outpatient basis. Reported adverse events and potential risks are described in Section 10. Appropriate dose modifications are described in Section 7. No investigational or commercial agents or therapies other than those described in Sections 6.1 and 6.3 may be administered with the intent to treat the patient's malignancy.

Study Regimen Description				
Agent	Dose	Route	Schedule	Cycle Length
Sn-117m-DTPA	20 mCi/70 kg (0.28 mCi/kg)	Slow IV injection over 10 min	Day 1	8 weeks*

\*Treatment continues for 2 cycles.

**Retreatment** after 2 cycles is allowed after an evaluation of AEs if:

- pain ( $\geq 4$  on 11-point intensity scale) recurs within 6 months after a 16-week pain observation period  
AND
- no disease progression on bone scans ( $\leq 2$  new bone lesions), or evidence of clinical progression (such as development of cancer-related symptoms)

Patients will be administered two additional cycles (8 weeks apart) if they meet the retreatment criteria. The maximum treatment dose per patient is four injections in this study.

Patients will be instructed to maintain a high fluid intake (drink at least two to three quarts of fluid every 24 hours) for 2 weeks after each Sn-117m-DTPA treatment to minimize a concentrated radioactive excretion. In general, drinking alcoholic beverages should be kept to a minimum or avoided completely. Patients will be educated on hygiene instruction/precautions on post-therapy treatment (see Appendix I).

Required Criteria for Each Re-Treatment:

Patients must have adequate organ and marrow function as defined below to be eligible for subsequent treatments after the first treatment administration:

- leukocytes	$\geq 2,000/\text{mcL}$
- absolute neutrophil count	$\geq 1,000/\text{mcL}$
- platelets	$\geq 75,000/\text{mcL}$
- hemoglobin	$\geq 8.0 \text{ g/dL}$
- total bilirubin	$\leq 2.5 \times \text{institutional ULN}$
- AST(SGOT)/ALT(SGPT)	$\leq 5 \times \text{institutional ULN}$
- creatinine*	$\leq 1.7 \text{ mg/dL}$
	OR
- glomerular filtration rate (GFR)	$\geq 50 \text{ mL/min}/1.73 \text{ m}^2$ (see Appendix B)

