## 6.3 General Concomitant Medication and Supportive Care Guidelines

### 6.3.1 Concomitant Prostate Cancer Therapy

- Patients receiving bisphosphonates or denosumab prior to enrollment can maintain therapy throughout all or part of the study. The bisphosphonate may be stopped or

started at the discretion of the investigator throughout the study (*i.e.*, both treatment phase and follow-up). Injection of bisphosphonates should be done at least 2 hours before or after study drug administration.

- Patients who have not undergone bilateral orchiectomy are allowed and should receive LHRH agonists or antiandrogen such as bicalutamide throughout the study (*i.e.*, both treatment phase and follow-up).
- Cytotoxic chemotherapy, androgen receptor blockers, androgen biosynthesis inhibitors, other systemic radioisotopes, hemi-body external radiotherapy, and other investigational drugs should not be used during the treatment period. These treatments can be given if at least 8 weeks after the last injection.
- Colony stimulating factors (*e.g.*, erythropoietin and granulocyte colony stimulating factors) and transfusions products (*e.g.*, red blood cell transfusion, and/or platelet transfusion) as dictated by standard practice are acceptable while the subject is enrolled in the study.

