### 8.1.2 Agent Ordering and Agent Accountability

**8.1.2.1** Sn-117m-DTPA is supplied by Serene LLC and distributed by IsoTherapeutics under a DCTD, NCI-sponsored IND.

- All requests for Sn-117m-DTPA must be submitted to IsoTherapeutics using the attached order request form attached in **Appendix L**. Complete all requested fields on the order request form. Obtain subject's weight prior to each dose. Requests must be submitted to IsoTherapeutics at least one week in advance of the planned administration date and must be shipped to the authorized facility address as identified on the Site On-Boarding Form and to a site shipping contact as identified on the Site On-Boarding Form. A copy of the completed order request form must be retained as a study record.

- Unused doses are to be accounted for on the NCI DARF. Unused doses may be destroyed following applicable agreement state and federal regulations for decay in storage for Sn-117m-DTPA.

The Authorized User investigator prescribing Sn-117m-DTPA must be registered with CTEP, DCTD through an annual submission of FDA Form 1572 (Statement of Investigator), NCI Biosketch, Agent Shipment Form, and Financial Disclosure Form (FDF), and be designated as such on the Site On-Boarding Form and the Delegation of Task Log.

**8.1.2.2 Agent Inventory Records** – The investigator, or a responsible party designated by the investigator, must maintain a careful record of the receipt, dispensing and final disposition of all agents received using the NCI Investigational Agent (Drug) Accountability Record (DARF) available on the CTEP forms page. Store and maintain separate NCI Investigational Agent Accountability Records for each agent, strength, formulation and ordering investigator on this protocol. **All Shipping Declaration Forms received with the Sn-117m-DTPA shipments are considered IND records and must be retained by the site along with the NCI Drug Accountability Records for the trial.**

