### 9. STATISTICAL CONSIDERATIONS

#### 9.1 Study Design/Endpoints

This is a single-arm, open-label phase 2 study to evaluate the efficacy of Sn-117m-DTPA on

sustained pain response in patients with CRPC metastatic to at least two bone sites, with at least one clinically meaningful pain at baseline ( $\geq 4$  on an 11-point pain intensity scale). Sustained pain-response is defined as: 1) achieving pain index  $\leq 3$  within a 12-week period and 2) maintaining that pain index  $\leq 3$  over a 16-week time period (beginning when the pain index  $\leq 3$  is initially achieved). The maximum duration of follow-up required to declare a patient a responder is 28 weeks, representing a patient who initially achieves pain index  $\leq 3$  toward the end of the 12-week period and is followed for an additional 16 weeks to confirm maintenance of pain index  $\leq 3$ .

Eligible patients will be assigned to receive Sn-117m-DTPA at 20 mCi/70 kg (0.28 mCi/kg) every 8 weeks for two cycles. Treatment will last for 16 weeks with two treatment injections given at 8-week intervals. The study utilizes a mini-max Simon two-stage design to assess anti-tumor activity and pain benefit of Sn-117m-DTPA.

Patients are not allowed to receive external radiation within 12 weeks from the start of treatment administration. If their pain index does not reach  $\leq 3$  after 12 weeks, they are not meeting the primary endpoint, and they can then get external radiation for pain control.

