#### 9.4.8 Clinical Progression-Free Survival

Clinical PFS will be calculated from the time of study enrollment until disease progression, which is defined as 1) symptomatic progression (increasing pain from a metastatic lesion); 2) progression of bone lesions assessed per PCWG3 criteria; or 3) progression of soft-tissue lesions

assessed per RECIST v1.1 criteria. PSA progression without progression on bone lesions nor symptomatic is not considered as clinical progression. Clinical PFS will be censored if clinical progression is not observed.

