A: Sn-117m-DTPA: 20 mCi/70 kg (0.28 mCi/kg) slow IV injection over 10 min on C1D1 and C2D1

\*Patients can be retreated if pain recurs within 6 months after 16-week pain observation period

a: Follow-up visit evaluation. Every 3 months or as clinically indicated up to one year from the first dose injection or disease progression

b: Albumin, ALP, total bilirubin, bicarbonate, BUN, calcium, chloride, creatinine, glucose, LDH, sodium, potassium, total protein, SGOT [AST], SGPT [ALT].

c: Pre-treatment daily baseline pain and analgesic use for 7 days (at least 4 out of 7 days) is required before treatment initiation. Patients will be asked to report their pain at its worst in the last 24 hours and analgesic use (stable/reduced/increased) by digital version every 2 weeks through Week 28, followed by routine clinic follow up or when they experience new pain during off-visit. **A full short version of brief pain inventory (BPI) will be asked at baseline, after Cycle 1, after Cycle 2, and at Week 24.**

d: PRO-CTCAE survey items will be assessed by digital instruments. Beginning at Week 28, surveys are requested every 3 months for 6 months after the last study treatment administration.

e: Serial DTPA dosimetry scans (optional) will be obtained at 1 hour, 4 hours (or within 4-6 hours), 24 hours (or within 16-24 hours), 48 hours (or within 36-48 hours), 72 hours (or within 60-72 hours), 1 week (+/2 days), and 4 weeks (+/2 days) post-infusion. The dosimetry scan will only be performed with first cycle of injection.

f: Urine collection for urinalysis will be collected at the indicated time points or as clinically indicated to monitor for microscopic or macroscopic hematuria as part of genitourinary toxicity monitoring.

g: Imaging: Follow up tumor response will be evaluated by CT scan of abdomen and pelvis, bone scan and chest X-ray. If Chest X-ray shows abnormal or clinically symptomatic, then CT chest should be obtained. Follow-up scans at every 8 weeks will be performed as clinically indicated, per institutional standards. PSMA PET CT scan at baseline is also acceptable.

*NCI Protocol #: 10437*

*Version Date: January 10, 2022*

h: Blood collections for research during Cycles 1 and 2 should be collected on the last day of each cycle.

i: CBC and serum chemistry should be performed 1 week before the start of Cycle 2.

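### Section 6.1 sets no minimum interval between other systemic therapy and the first retreatment injection

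*Combined protocol and SAP*

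**What the plan says.** Section 6.1 permits retreatment after an adverse-event evaluation. Pain of at least 4 must recur within 6 months after a 16-week observation period, with no bone-scan or clinical progression. A separate list of organ and marrow limits applies to every injection after the first. If the criteria are met, "Patients will be administered two additional cycles (8 weeks apart) if they meet the retreatment criteria", and "The maximum treatment dose per patient is four injections in this study". Section 6.4 and the study calendar restate the rule ("Patients can be retreated if pain recurs within 6 months after 16-week pain observation period") and add no interval since other therapy. Section 7 adds recovery rules for toxicity, but no interval either.

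Section 6.3.1 lists therapies closed to patients on treatment: chemotherapy, androgen receptor blockers, androgen biosynthesis inhibitors, and "other systemic radioisotopes, hemi-body external radiotherapy, and other investigational drugs should not be used during the treatment period". It then says "These treatments can be given if at least 8 weeks after the last injection". It does not say whether this is injection 2, the most recent injection, or the final one the patient receives.

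The only stated washouts are the exclusions in Section 3.2. They run back from study entry (3.2.4: chemotherapy, immunotherapy, external radiotherapy, 4 weeks) or from the start of study treatment (3.2.5: other bone-seeking radionuclides, 24 weeks; 3.2.7: investigational agents, 4 weeks).

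**The concern.** The protocol judged these intervals necessary before injection 1 but does not carry them to injection 3. If therapies reopen 8 weeks after injection 2, a patient may receive one and then meet every retreatment criterion sooner after it than the entry rules would have allowed.

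Bone-scan or clinical progression bars retreatment, so the affected patient needs another reason for new therapy. PSA-only progression is one, because Section 9.4.8 says "PSA progression without progression on bone lesions nor symptomatic is not considered as clinical progression".

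At stake is marrow safety in retreated patients and the interpretation of descriptive data after injections 3 and 4. Section 2.2.6 warns that prior cytotoxic chemotherapy may deepen marrow suppression. The same section says earlier studies do not point to severe myelotoxicity, and Section 2.3 describes this agent's marrow toxicity as low relative to beta and alpha emitters. The expected harm is therefore modest.

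**Working it through.** The plan states no retreatment interval, so there is no figure of its own to reproduce. The check compares the provisions and then does week arithmetic.

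**Step 1. Intervals side by side.**

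| Earlier therapy | Before entry or injection 1 | Before injection 3 |
|---|---|---|
| Chemotherapy, immunotherapy, external radiotherapy | 4 weeks (3.2.4) | none stated |
| Other bone-seeking radionuclide | 24 weeks (3.2.5) | none stated |
| Investigational agent | 4 weeks (3.2.7) | none stated |

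**Step 2. When other therapies open.** Injections fall at Weeks 0 and 8 (9.1). If the last injection is injection 2, therapies open at 8 + 8 = Week 16. If it is the patient's final study injection, they stay closed to a retreated patient until after injection 4, and no gap arises.

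**Step 3. Earliest injection 3.** Let S be the week in which the 16-week observation period starts. Section 6.1 does not fix S. Section 9.1 measures maintenance of response "over a 16-week time period (beginning when the pain index" first reaches 3 or less, which must happen within 12 weeks. Pain is reported every 2 weeks (5.10.2.2.2), so on that basis S runs from 2 to 12. Section 8.1.2 adds one week: "Requests must be submitted to IsoTherapeutics at least one week in advance of the planned administration date". Assume that pain recurs, and the dose is ordered, on the day the window opens.

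Window opens = S + 16. Earliest injection 3 = S + 17. Gap from Week 16 = S + 1.

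| Start S | Window opens | Injection 3 | Gap from Week 16 |
|---|---|---|---|
| 2 (9.1, earliest) | 18 | 19 | 3 weeks |
| 4 | 20 | 21 | 5 weeks |
| 12 (9.1, latest) | 28 | 29 | 13 weeks |
| 0 (alternative: first injection) | 16 | 17 | 1 week |
| 16 (alternative: end of cycle 2) | 32 | 33 | 17 weeks |

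Every gap is below 24 weeks. Meeting the entry interval after a Week 16 radionuclide would need injection 3 no earlier than 16 + 24 = Week 40.

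**Step 4. Later recurrence.** Taking 6 months as 26 weeks, the recurrence window closes at 18 + 26 = Week 44 to 28 + 26 = Week 54. Recurrence at the close puts injection 3 at least 44 − 16 = 28 to 54 − 16 = 38 weeks after a Week 16 radionuclide, beyond 24. The shortfall therefore concerns earlier recurrences, or radionuclides given later than Week 16.

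**Step 5. The 4-week interval.** A single Week 16 dose clears 4 weeks at Week 20. Among the 9.1 starts, only S = 2 with recurrence on the opening day gives an earlier injection 3 (Week 19). On the 2-weekly schedule the first report after Week 18 is Week 20, so injection 3 falls at 20 + 1 = Week 21. The gap is then 5 weeks and the rule is met. An unscheduled report of new pain (calendar note c) could come sooner. A Week 0 start would give 18 + 1 − 16 = 3 weeks, but recurrence presupposes a response, so that is the least natural reading.

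Repeated dosing is different. For injection 3 at Week 21, any dose after 21 − 4 = Week 17 is too recent; at Week 29, any dose after 29 − 4 = Week 25. Chemotherapy started after Week 16 and still running as the window opens would breach the interval.

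**Step 6. Frequency.** The documents give no rate of such therapy. One patient is 1/25 = 4%.

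**The case against.** The strongest reply is that the plan deliberately uses status-based rules for later injections: adverse-event evaluation, no progression, laboratory limits, haematological recovery to grade 1 in Section 7 and investigator judgment in 6.4. It gives no reason why 24 weeks must carry over. This stands in part, since these checks do reduce the risk. They show only current status, however, and two limits are looser than at entry: platelets 75,000 against 100,000/mcL, and hemoglobin at least 8.0 against above 10.0 g/dL. The neutrophil limit is unchanged, and a leukocyte limit is added. In the phase 1/2 study (2.2.4.1), mean nadirs came at 34 days for white cells and 41 days for platelets. If another radionuclide behaves similarly, which is an assumption, acceptable counts at 3 weeks (21 days) could precede the nadir.

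A second reply is that 6.1 bars anticancer therapy not described in 6.1 or 6.3, and 3.2.7 also excludes patients scheduled for an investigational agent during planned treatment. Neither sets an interval, and 6.3.1 itself describes and reopens the therapies at issue.

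Third, a second bone-seeking radionuclide in a patient without progression is unlikely. Section 6.4 also lists disease progression separately from clinical progression, so 9.4.8 does not settle whether PSA progression leaves retreatment open. Both points stand. The radionuclide case is the larger shortfall but the less likely one.

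A reader might infer that a Week 16 chemotherapy dose ordinarily breaches the 4-week interval. Step 5 shows that it seldom would. A reader might also extend the point to focal external radiotherapy. The documents do not support that: 6.3.1 does not name it, 9.1 has its own rule, and 3.1.5 and 3.2.4 conflict on it.

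**Conclusion.** The omission is real and worth a short amendment. Followed as written, the retreatment rule can allow injection 3 at an interval the protocol forbids before injection 1. This depends on reading the last injection in 6.3.1 as injection 2. That is the practical reading, because at Week 16 a site cannot know who will be retreated.

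For a Week 16 radionuclide the gap is about 3 to 13 weeks against 24, given the 9.1 start and recurrence as the window opens. Later recurrence lengthens it. For chemotherapy or an investigational agent, the realistic shortfall is a last dose within 4 weeks of injection 3, after treatment begun later than Week 16.

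A reader might infer that the protocol intends such sequences, or that serious marrow harm is expected. The documents support neither. They leave the sequence unaddressed, and 2.2.6 and 2.3 suggest modest harm. Few of the 25 patients are likely to be affected. Sample size and the DLT rule do not change. That therapies opening at Week 16 could fall inside the pain-maintenance period (ending Weeks 18 to 28) is a separate matter, which this fix does not resolve.

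**What to change.** Add one criterion to 6.1: before the first retreatment injection, no systemic radionuclide within 24 weeks, and no chemotherapy, immunotherapy, hemi-body radiotherapy or investigational agent within 4 weeks. State in 6.3.1 that the last injection means the most recent study injection, and that these therapies are barred again once retreatment starts.

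Do not define it as the final study injection. That would keep chemotherapy and androgen-pathway drugs closed to potentially retreatable patients until about Week 44 to 54, when the recurrence window ends. It would also contradict the washout criterion, which presupposes that such therapy may be given between courses.

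The cost is two short text changes and a few delayed retreatments. After a Week 16 radionuclide, injection 3 could be given from Week 40. The 6-month limit in 6.1 applies to recurrence of pain rather than to the injection date, so that patient is delayed, not excluded by the limit.

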\*Should a 40% increase over the baseline serum creatinine value occur during the course of treatment, with a concomitant decrease of over 40% in creatinine clearance as calculated from serum creatinine concentrations according to Cockcroft's method (see Appendix B), patients must also have a measured creatinine clearance (or GFR) performed, unless resolved within 16 weeks.

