## 7. DOSING DELAYS/DOSE MODIFICATIONS

No Sn-117m-DTPA dose modification is allowed. Patients will be monitored continuously for AEs throughout the study. Patients must be instructed to notify their physician immediately for any and all side effects. Treatment interval is scheduled every 8 weeks or every 56 days with a window period of +/- 7 days for all time points. If the treatment needs to be delayed due to an adverse event, study drug administration can be delayed up to 8 weeks for recovery, with the following conditions:

- Hematological toxicities must resolve to CTCAE grade 1 or less (or, if abnormal at baseline, not more than one grade above baseline) prior to administration of the next Sn-117m-DTPA dose. In the absence of recovery after 4 weeks, patients are to discontinue further study drug administrations.
- Non-hematological toxicities must resolve to CTCAE grade 2 (gastrointestinal events) or grade 3 (other toxicities) prior to administration of the next dose.
- If patients experience spinal cord compression during the treatment phase, Sn-117m-DTPA administration can continue with up to a 4-week delay if the patient is adequately treated with steroids, local SBRT, or surgery.
- If patients experience traumatic fracture in weight-bearing bones during the treatment phase, the study drug administration should be delayed 4 weeks from the fracture.

As a general approach, it is suggested that all AEs be managed with supportive care when possible at the earliest signs of toxicity.

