## APPENDIX B FORMULA TO ESTIMATE RENAL FUNCTION USING SERUM CREATININE

Formulas to estimate renal function using serum creatinine provided by the NCI's Investigational Drug Steering Committee (IDSC) Pharmacological Task Force in table below.

1. Estimated glomerular filtration rate (eGFR) using the Chronic Kidney Disease Epidemiology Collaboration (CKD-EPI) (Levey *et al.*, 2009).

Formulae:

Race and Sex	Serum Creatinine (SCr), $\mu\text{mol/L}$ ( $\text{mg/dL}$ )	Equation
Black	Female $\leq 62$ ( $\leq 0.7$ )	$\text{GFR} = 166 \times (\text{SCr}/0.7)^{-0.329} \times (0.993)^{\text{Age}}$
	$> 62$ ( $> 0.7$ )	$\text{GFR} = 166 \times (\text{SCr}/0.7)^{-1.209} \times (0.993)^{\text{Age}}$
	Male $\leq 80$ ( $\leq 0.9$ )	$\text{GFR} = 163 \times (\text{SCr}/0.9)^{-0.411} \times (0.993)^{\text{Age}}$
	$> 80$ ( $> 0.9$ )	$\text{GFR} = 163 \times (\text{SCr}/0.9)^{-1.209} \times (0.993)^{\text{Age}}$
White or other	Female $\leq 62$ ( $\leq 0.7$ )	$\text{GFR} = 144 \times (\text{SCr}/0.7)^{-0.329} \times (0.993)^{\text{Age}}$
	$> 62$ ( $> 0.7$ )	$\text{GFR} = 144 \times (\text{SCr}/0.7)^{-1.209} \times (0.993)^{\text{Age}}$
	Male $\leq 80$ ( $\leq 0.9$ )	$\text{GFR} = 141 \times (\text{SCr}/0.9)^{-0.411} \times (0.993)^{\text{Age}}$
	$> 80$ ( $> 0.9$ )	$\text{GFR} = 141 \times (\text{SCr}/0.9)^{-1.209} \times (0.993)^{\text{Age}}$

SCr in  $\text{mg/dL}$ ; Output is in  $\text{mL/min}/1.73 \text{ m}^2$  and needs no further conversions.

2. eGFR using the Modification of Diet in Renal Disease (MDRD) Study (Levey *et al.*, 2006).

$175 \times \text{SCr}^{-1.154} \times \text{age}^{-0.203} \times 0.742$  (if female)  $\times 1.212$  (if black)  
Output is in  $\text{mL/min}/1.73 \text{ m}^2$  and needs no further conversions.

3. Estimated creatinine clearance (ClCr) by the Cockcroft-Gault (C-G) equation (Cockcroft and Gault, 1976).

[figure not shown]
$$\text{CLcr (mL/min)} = \frac{[140 - \text{age (years)}] \times \text{weight (kg)}}{72 \times \text{serum creatinine (mg / dL)}} \times 0.85 \text{ for female patients}$$

Followed by conversion to a value normalized to  $1.73 \text{ m}^2$  with the patient's body surface area (BSA).

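### The renal footnote for re-treatment pairs a 40% creatinine rise with a Cockcroft clearance fall of over 40%, which at stable weight needs a rise above 66.7%; its 16-week waiver is twice the dosing interval

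*Combined protocol and SAP*

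**What the plan says.** Section 6.1 lists laboratory criteria for every dose after the first: "Patients must have adequate organ and marrow function as defined below to be eligible for subsequent treatments after the first treatment administration". The renal criterion there is creatinine ≤1.7 mg/dL or GFR ≥50 mL/min/1.73 m².

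A footnote on creatinine adds a rule on change from baseline. It opens "Should a 40% increase over the baseline serum creatinine value occur during the course of treatment" and continues "with a concomitant decrease of over 40% in creatinine clearance as calculated from serum creatinine concentrations", by Cockcroft's method with a pointer to Appendix B. If both conditions are met, a measured creatinine clearance or GFR must also be done, "unless resolved within 16 weeks".

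Appendix B lists as its third formula "Estimated creatinine clearance (ClCr) by the Cockcroft-Gault (C-G) equation": (140 − age) × weight ÷ (72 × serum creatinine), then normalised to 1.73 m² of body surface area (BSA).

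Section 7 sets the treatment interval at 8 weeks, ±7 days, and for an adverse event allows that "study drug administration can be delayed up to 8 weeks for recovery". Section 9.1 gives the planned treatment period as 16 weeks with two injections. Section 6.1 allows two further injections on retreatment, also 8 weeks apart.

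**The concern.** The same percentage is attached to two measures that do not move by the same percentage. In the Cockcroft formula creatinine is the only term that changes quickly, and it is in the denominator, so the two limbs restate one measurement. When both must be met, the stricter one decides and the other does nothing. A site that reads the first limb would expect a check at +40%; the second limb withholds it until a much larger rise.

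The waiver raises a separate difficulty. The footnote belongs to criteria that must be settled before a dose, but its exception looks 16 weeks ahead.

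What is at stake is whether a confirmatory renal measurement is made, and made consistently across sites, before a further injection. Section 10.3.4 makes grade 3 or higher renal and genitourinary events expedited, including suspected radiation nephropathy. Section 2.2.6 notes reversible nephrotoxicity with a related chelating agent in large repeated doses.

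**Working it through.** **Inputs.** From the Section 6.1 footnote: rise r = 40%, fall f of over 40%, both required, waiver 16 weeks. From Appendix B: the Cockcroft-Gault formula with BSA normalisation. From Sections 6.1 and 7: interval 8 weeks ±7 days, maximum delay 8 weeks.

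**Step 1: what a given creatinine rise does to clearance.** At fixed age and weight everything except creatinine cancels, BSA included, so new clearance ÷ old clearance = 1 ÷ (1 + r) and the fall is 1 − 1 ÷ (1 + r).

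| Creatinine rise | Fall in Cockcroft clearance |
|---|---|
| 40% | 1 − 1/1.4 = 28.6% |
| 50% | 1 − 1/1.5 = 33.3% |
| 60% | 1 − 1/1.6 = 37.5% |
| 66.7% | 1 − 1/1.667 = 40.0% |
| 70% | 1 − 1/1.7 = 41.2% |

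The footnote's pairing of 40% with over 40% is not reproduced. Sixteen weeks of ageing moves the 28.6% only to 28.8–29.0% (checked for assumed men aged 55, 70 and 82).

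**Step 2: what rise gives a 40% fall.** 1 ÷ (1 − 0.40) − 1 = 66.7%. The second limb fires only above that, and by then the first limb has already been met.

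**Step 3: weight loss.** Weight is taken before each dose (Section 8.1.2), so it can enter the calculation. For a fractional loss w, the rise needed is (1 − w) ÷ 0.6 − 1 for unnormalised clearance. With BSA normalisation it is √(1 − w) ÷ 0.6 − 1, on the assumption that BSA varies with the square root of weight at fixed height.

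- 5% loss: 0.95/0.6 − 1 = 58.3%; normalised, 0.9747/0.6 − 1 = 62.4%.
- 10% loss: 0.90/0.6 − 1 = 50.0%; normalised, 0.9487/0.6 − 1 = 58.1%.

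The effective trigger is then about +50% to +62%, still above the stated 40%.

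**Step 4: the other Appendix B formulas.** The footnote names Cockcroft, but the alternatives do not align the figures either. At +40%, CKD-EPI (male, creatinine above 0.9 mg/dL) falls 1 − 1.4^−1.209 = 33.4% and MDRD falls 1 − 1.4^−1.154 = 32.2%. A 40% fall needs rises of 52.6% and 55.7%.

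**Step 5: who falls in the gap.** A 40% rise stays within 1.7 mg/dL for baselines up to 1.7/1.4 = 1.21 mg/dL. A 66.7% rise does so for baselines up to 1.7/1.667 = 1.02 mg/dL. For example, 1.0 to 1.6 mg/dL is a 60% rise. The Cockcroft fall is 37.5%, no measurement is required, and 1.6 meets the absolute limit.

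**Step 6: the waiver.** 16 ÷ 8 = 2. An on-time Cycle 2 falls at week 7 to 9, so any rise since the first injection is at most 9 weeks old and still inside the 16 weeks. Only with the full delay does the dose reach that point: 8 + 8 = 16. The same holds between the two retreatment injections. Before the third injection the gap may be longer. The footnote does not define resolution or say from when the 16 weeks run.

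**The case against.** The strongest reply is that the rule is redundant rather than contradictory. Both conditions can be met together; the clearance limb simply governs. That stands. A reader might infer that the footnote cannot operate, or that +40% creatinine was the intended trigger. The documents support neither: the footnote attaches 40% to both measures and does not say which was meant.

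Second, the footnote decides little by itself. It adds a measurement and attaches no stop, delay or pass mark to the result. The 1.0 to 1.6 example therefore shows a missed test, not a changed dosing decision. That also stands.

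Third, a reader might infer that patients in the gap are re-dosed with no other renal protection. That is wrong. Creatinine is scheduled through Cycle 1 and again one week before Cycle 2 (Section 11, notes b and i). The absolute criterion applies at each later dose. The DLT definition (6.2), discontinuation for DLT or on investigator judgment (6.4) and the delay conditions (7) remain, and retreatment requires an evaluation of adverse events (6.1). None of these restates the 40% trigger, so they limit the harm without repairing the footnote.

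Fourth, the waiver might be read as permission to dose with an unresolved rise. It is not: it waives a measurement, and the Section 6.1 criteria still apply at each dose. Sixteen weeks also matches the planned treatment period. Neither fact tells a site at week 8 whether the measurement is due.

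Fifth, the protocol's dosimetry lowers the stakes. Section 2.2.3.1 reports very faint renal activity and a bone-to-kidney absorbed-dose ratio above 300. Appendix J's kidney figure gives 0.000159 Gy/MBq × 740 MBq ≈ 0.12 Gy for 20 mCi. This bears on priority, not on the arithmetic.

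**Conclusion.** The point holds as a should-fix. At stable weight the two limbs are one quantity at +40% and +66.7%. The 40% creatinine limb is redundant, and rises of 40% to about 66% do not lead to the measured clearance. With 5–10% weight loss the upper end of that gap comes down to about 50–62%. The stable-weight figures rest only on Appendix B's formula; the normalised weight-loss figures also rest on the square-root assumption for BSA.

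The waiver, at twice the interval, cannot be applied at an on-time next dose to a rise that began after the previous injection.

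A reader might go further and call the two absolute limits, creatinine 1.7 mg/dL and GFR 50, contradictory. They are joined by OR, so either suffices, and this point makes no claim about them. The primary endpoint and the two-stage decision rule are unaffected.

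**What to change.** The sponsor should reconcile two things in the Section 6.1 footnote.

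1. **The two 40% figures.** Either state the trigger in one measure, or give both limbs at equivalent values at stable weight: a 40% creatinine rise equals a 28.6% Cockcroft fall, and a 40% Cockcroft fall equals a 66.7% creatinine rise.
2. **The 16-week clause and the 8-week interval.** Make clear how the clause works when a dose falls due inside the 16 weeks, from when the period runs, and what counts as resolved.

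Which threshold and which clinical rule apply is for the sponsor to decide; none is proposed here. The cost is a wording change in an amendment. The possible downside is a few extra measured clearances, a test the footnote already provides for.
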